In this pilot clinical study we propose to conduct a prospective, randomized, double-blinded, placebo-controlled clinical trial, in 50 human subjects with CLI who have undergone a major (above-knee or below-knee) lower extremity amputation. 25 patients will receive NAC 1200mg intravenously twice a day for 6 consecutive days following amputation. 25 patients will receive placebo saline intravenous infusion twice a day for 6 days following amputation. Post-amputation patients will be monitored for specific anthropometric parameters and stump perfusion assessments (using laser-assisted fluorescent angiography and transcutaneous oxygen pressure measurement). **The primary study endpoints are to determine if lower extremity stump healing and perfusion are affected by perioperative NAC administration. A secondary endpoint will be to determine the effect size that would be necessary to power a larger clinical trial to determine whether NAC treatment can affect tissue perfusion and healing at major lower extremity amputation stumps in patients with CLI.**

Subject Selection and Withdrawal

Inclusion Criteria

Inclusion criteria for recruited subjects will be as follows:

- Subject undergoing elective major (above-knee or below-knee) lower extremity amputation for CLI
- Both male and female patients
- All ethnic groups
- Between of the ages of 30-90 years old

1.a Exclusion Criteria

Exclusion criteria for patients will be as follows:

- Pregnant women, and women who are breastfeeding
- Known history of end-stage liver disease
- Severe asthma
- Heavy alcohol consumption (male > 2 drinks per day and women > 1 drink per day)
- Individuals actively receiving chemotherapy.

- Anticipated enrollment in another study that investigates another drug agent within 30 days from enrollment in this study.
- Patients receiving carbamazepine.
- Severe anemia (HCT < 22).
- Allergy to either NAC or ICG

All inclusion and exclusion criteria will be verified from patient chart in Epic and through self report and/or LAR report; in particular, alcohol consumption and participation in another drug research study to obtain the most current information. **Email correspondence between RC, PI, and other study team members regarding patient enrollment may be included in the subjects chart to serve as a real time documentation of PI's approval to enroll participant, in addition to signature in CRFs.**

Ethical Considerations

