Upon consent and enrollment in the study, relevant subject information will be relayed to the Barnes Jewish Hospital (BJH) Investigational Pharmacy. Prior to proceeding to the operating room for lower extremity amputation, the patients will be randomized 1:1 by the BJH Investigational Pharmacy to either placebo saline infusion (twice daily) or a standard adult intravenous dose of NAC (1200mg twice daily) for 6 days post-amputation during the usual post-operative inpatient extremity off-loading and stump monitoring period. The pharmacy will maintain blinding, with no member of the investigational team having access to the record until the conclusion of the trial.

Early Withdrawal of Subjects

Patients unable to tolerate the administration of the drug will be withdrawn from the study at any point during their hospitalization and will continue to be monitored until their condition stabilizes. Patients unable to participate in the Post-operative Day 0 Non-invasive Laser Assisted Fluorescence Angiography (LAFA) will be withdrawn from the study at that time point and will not receive the investigational product. Subjects for which continuous IV access is not medically indicated during the 6 day study drug administration period may be withdrawn from the study. Patients unable to participate in follow-up appointments will also be withdrawn from the study.

When and How to Withdraw Subjects

Patients unable to tolerate the administration of the drug will be withdrawn from the study trial at any point during their hospitalization. Patients unable to participate in follow-up appointments will also be withdrawn from the study. They will continue to be monitored for adverse events as inpatients for the duration of their hospitalization. Patients unable to participate in the Post-operative Day 0 Non-invasive Laser Assisted Fluorescence Angiography (LAFA) will be withdrawn from the study at that time point and will not receive the investigational product. No further study follow up will be required.

Data Collection and Follow-up for Withdrawn Subjects

Patient data will be collected up until time of withdrawal from the study and pooled into the collective analysis along with all other patients.

Study Drug

Description

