N-acetyl cysteine (NAC) ((2R)-2-acetamido-3-sulfanylpropanoic acid) is an amino acid derivative of L-cysteine, which is a precursor to glutathione and cysteine. Historically, NAC has been used to treat acetaminophen overdose [6], as well as mucous secretions in patients with cystic fibrosis or chronic obstructive pulmonary disease [24].

Pharmacokinetics including the following [24] :

Distribution: The steady-state volume of distribution (V_{dss}) and the protein binding for acetylcysteine were reported to be 0.47 liter/kg and 83%, respectively.

Metabolism: N-acetyl-cysteine may form cysteine, disulfides, and conjugates in vivo (N, N'-diacetylcysteine, N-acetyl cysteine-cysteine, N-acetyl cysteine-glutathione, N-acetyl cysteine-protein, etc). Based on published data, it was reported that after an oral dose of 35S-acetylcysteine, about 22% of total radioactivity was excreted in urine after 24 hours. No metabolites were identified.

Elimination: After a single intravenous dose of N-acetyl cysteine, the plasma concentration of total N-acetyl cysteine declined in a poly-exponential decay manner with a mean terminal half-life (T_{1/2}) of 5.6 hours. The mean clearance (CL) for N-acetyl cysteine was reported to be 0.11 liter/hr/kg and renal CL constituted about 30% of total CL.

Treatment Regimen

Upon study enrollment, patients will be randomized 1:1 by BJH Investigational Pharmacy to either placebo ½ normal saline infusion (twice a day) or a standard adult intravenous dose of NAC (1200mg twice a day) for 6 days post-amputation. The BJH Investigational Pharmacy will perform this with knowledge of the patient's medical record number (MRN), and without knowledge of any pre-existing medical conditions, comorbidities, past medical history, prior interventions, etc. The first infusion will be administered within three hours from leaving the operating room. The second infusion will be a minimum of 6 hours after the first infusion, or at 21:00 in an attempt to be consistent with routine hospital BID dosing times. Patients will receive their scheduled infusions as long as they are hospitalized according to the chart below (Table 1). **If medication is not administered within that window, dose will not be given to not interfere with the rest of the doses.**

Table 1:

Post-operative Day (POD)	Infusion Schedule
POD 0	1. Within 3 hours from the conclusion of the operation 2. Approximately 6 hours after first infusion, or at 21:00 +/- 6 hours

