- **Day 0 (Day of Operation):** If possible and/or equipment available, obtained prior to the operation at the anticipated level of the amputation.
- **Postoperative Day3:** If possible and/or equipment available, obtained following dressing removal at bedside in the inpatient hospital unit.
- **Postoperative Day5:** If possible and/or equipment available, also obtained at bedside in the inpatient hospital unit if the patient is still in-house.

[figure not shown]
Contraindications to Measurement:

- Patient refusal/inability to participate in measurement before or during data collection
- Patient SpO₂ < 92%, Patient is febrile >38°C, unstable vitals
- Patient unable to lie supine for at least 20 minutes during measurement collection
- Patient unable to breathe normobaric oxygen
- *A contraindication to TcPO₂ measurements does not exclude the patient from other measurements within the study protocol

Protocol Steps:

1. Ensure patient meets the eligibility criteria above.
2. Keep patient covered, and expose the anticipated amputation site or at the amputation stump. Do not elevate the site throughout the measurement collection.
3. Select 4 collection sites as follows:
 1. 3 sites on the anticipated amputation site the stump site, one per section. (Figure 1)
 2. 1 control site on the left anterior chest in indicated on figure. (Figure 1)
4. Electrodes will be placed as per TCM Manual instructions, replicated below with the following specifications:
 1. Temp. set to 45°C.
 2. Do not place probes on scar tissue or dermatologically compromised sites.
 3. Do not place probe over bone.
5. After 15-20 minutes, record the TcPO₂ numbers in all 4 sites. Mark the location of the sites for future measurements to ensure a consistent location for measurement and control (days 2 and 4).
6. Remove probes from patients.

Figure 1

listed

or at

area

Data Analysis:

After TcPO₂ measurements have been collected, the 3 amputation site measurements will be averaged to calculate a mean TcPO₂. The control site measurement on the operated leg will be used to calculate a Regional perfusion index (Mean TcPO₂ / Chest/Control TcPO₂). The non-operated leg measurement site (compared against the operated site) will be used to determine if lower TcPO₂ values in the amputation site are due to regional or systemic oxygenation.

How to place an electrode

Step	Action
------	--------

1. Calibrate the tcpO₂ electrode.

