All AEs will be recorded in the CRF from the time of consent through the 30 days post-operative visit however all AEs will be followed to resolution or stabilization.

Study Outcome Measurements and Ascertainment

As described previously, study subjects will undergo evaluations using LAFA, TcP02, and anthropometric measurements.

Statistical Plan

Sample Size Determination and Power

The purpose of this study is to obtain sufficient preliminary data to determine the sample size necessary for a future large definitive clinical trial. For this pilot study, we plan to enroll 25 patients in each group, allowing for a dropout rate of 10% per group.

We emphasize that effect size (the expected difference in primary outcome between the treatment and control groups) should not be determined by the pilot study. Rather it is determined by the minimum clinically important difference. However, the effect size from the pilot give us some ideas about possible achievable difference.

Interim Monitoring and Early Stopping

An interim analysis will be conducted once >30 patients are enrolled in the study. Analysis will focus on determining differences between NAC and control group. Interim analysis will help determine early differences between the study groups and safety profile of study intervention. The investigators may end the study early depending on study findings, safety profile of the data, and/or if data is adequate for a peer-reviewed publication.

Analysis Plan

Data analysis include (1) the partition of variation of outcome measurements into within and between patient components to obtain standard deviation of measurements, intra-class correlation of the measurements, (2) use of appropriate regression model (GEE or mixed effect regression) to compare the outcome measurements between two groups, while accounting for the intra-class correlation. Interpretation of analysis should be made within the context of a pilot study where we have a pre-specified hypothesis but do not have power analysis for testing the hypothesis.

Statistical Methods

One of the main study outcomes (and in the future large study) is the stump perfusion assessment, which is a continuous variable measured three times (D0, D3, and D5) after

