 23. Kapp, M.B., *Ethical and legal issues in research involving human subjects: do you want a piece of me?* J Clin Pathol, 2006. **59**(4): p. 335-9.
 24. Holdiness, M.R., *Clinical pharmacokinetics of N-acetylcysteine.* Clin Pharmacokinet, 1991. **20**(2): p. 123-34.

STATISTICAL ANALYSIS PLAN

**Protocol Title: N-Acetyl-Cysteine for Healing of
Amputation Stumps in the Setting of Diabetes**

NCT03253328

**Protocol Version 11.0
Date: March 26, 2020**

Statistical Plan

Sample Size Determination and Power

The purpose of this study is to obtain sufficient preliminary data to determine the sample size necessary for a future large definitive clinical trial. For this pilot study, we plan to enroll 25 patients in each group, allowing for a dropout rate of 10% per group.

We emphasize that effect size (the expected difference in primary outcome between the treatment and control groups) should not be determined by the pilot study. Rather it is determined by the minimum clinically important difference. However, the effect size from the pilot give us some ideas about possible achievable difference.

Interim Monitoring and Early Stopping

An interim analysis will be conducted once >30 patients are enrolled in the study. Analysis will focus on determining differences between NAC and control group. Interim analysis will help determine early differences between the study groups and safety profile of study intervention. The investigators may end the study early depending on study findings, safety profile of the data, and/or if data is adequate for a peer-reviewed publication.

Analysis Plan

Data analysis include (1) the partition of variation of outcome measurements into within and between patient components to obtain standard deviation of measurements, intra-class correlation of the measurements, (2) use of appropriate regression model (GEE or mixed effect regression) to compare the outcome measurements between two groups, while accounting for the intra-class correlation. Interpretation of analysis should be made within the context of a pilot study where we have a pre-specified hypothesis but do not have power analysis for testing the hypothesis.

Statistical Methods

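### Above-knee and below-knee amputations are both eligible, but neither the allocation nor the primary model accounts for amputation level, which adds avoidable noise to arms of 25

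*Combined protocol and SAP*

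**What the plan says.** Under Inclusion Criteria the first condition reads "Subject undergoing elective major (above-knee or below-knee) lower extremity amputation for CLI", so two kinds of stump enter one comparison. Under Randomization Method and Blinding, "the patients will be randomized 1:1 by the BJH Investigational Pharmacy" before surgery. The same paragraph says that "relevant subject information will be relayed to the Barnes Jewish Hospital (BJH) Investigational Pharmacy", without defining that information. Under Treatment Regimen the protocol adds: "The BJH Investigational Pharmacy will perform this with knowledge of the patient's medical record number (MRN), and without knowledge of any pre-existing medical conditions". No section names a stratification factor, a block scheme or minimisation.

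The Analysis Plan, identical in the protocol and the SAP, calls for "use of appropriate regression model (GEE or mixed effect regression) to compare the outcome measurements between two groups" and names no covariate. The sample size statement is "we plan to enroll 25 patients in each group, allowing for a dropout rate of 10% per group", and the plan concedes that "we have a pre-specified hypothesis but do not have power analysis for testing the hypothesis".

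The planned level is known before surgery. The day 0 TcPO₂ reading, when it can be taken, is to be "obtained prior to the operation at the anticipated level of the amputation".

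**The concern.** Both primary aims are measured at the stump: perfusion by postoperative day 5 and healing over 30 days. Level decides where on the limb the stump lies, and it is plausible, though the documents do not say so, that perfusion and healing differ between thigh and below-knee stumps. If they do, a chance difference in level mix moves the observed arm difference by the size of the imbalance times the effect of level. Neither the design nor the model limits that.

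Two features raise the stakes. First, an interim analysis after more than 30 enrolments is unblinded, looks for differences between arms, and lets the investigators end the study on what they see. Imbalance is likelier at that size. Second, the pilot exists to supply variance, within-patient correlation and outcome level by arm for a later trial. Without a level term, the between-patient variance includes whatever difference lies between the two levels.

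**Working it through.** **The plan's own figure.** No alpha, power, effect size or SD is stated, so 25 per arm cannot be derived from a power formula. The dropout arithmetic is consistent: 25 × 0.9 = 22.5, and 22 / 0.9 = 24.4, which rounds up to 25. The plan thus expects about 22 completers per arm.

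**Inputs.** From the documents: 25 per arm, 1:1, no stratification, and an interim look at just over 30 enrolled (taken as 15 per arm). Assumed: above-knee share 20%, 30%, 40% or 50%; difference between levels 0.5 or 1 within-level SD.

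**Step 1: spread of the imbalance.** With n per arm and K above-knee cases among 2n patients, the number X in one arm is hypergeometric. The gap in shares is (2X − K)/n, with SD = 2·√[p(1 − p)/(2n − 1)], where p = K/2n. For n = 25 and p = 0.30 this is 2·√(0.21/49) = 0.131, or 13 points. At shares of 20/30/40/50% the SD is 11/13/14/14 points.

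**Step 2: chance of a gap of 20 points or more.** This means 5 or more patients at 25 or 22 per arm (5/22 is 23 points), and 3 or more at 15 per arm.

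| Per arm | Method | 20% | 30% | 40% | 50% |
|---|---|---|---|---|---|
| 25 | hypergeometric | 7% | 22% | 15% | 26% |
| 25 | independent binomials | 11% | 16% | 19% | 20% |
| 22 | hypergeometric | 13% | 19% | 12% | 13% |
| 22 | independent binomials | 9% | 14% | 17% | 17% |
| 15 | hypergeometric | 17% | 43% | 26% | 47% |
| 15 | independent binomials | 25% | 32% | 35% | 36% |

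The hypergeometric rows jump because the gap in counts always has the same parity as K. With odd K a gap of exactly 5 (or 3) can occur; with even K the next possible gap is 6 (or 4). At 25 per arm, K = 14, 15 and 16 give 11%, 22% and 13%. The binomial rows let K vary and are the steadier guide.

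**Step 3: shift in the arm difference.** Shift = gap × level effect. A 20-point gap gives 0.20 × 0.5 = 0.10 SD or 0.20 × 1 = 0.20 SD. For one measurement per patient at 25 per arm, the standard error of the difference is √(2/25) = 0.28 SD, so the shift is 0.35 or 0.71 of a standard error.

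**Step 4: variance carried forward.** Mixing two levels that differ by d within-level SDs adds p(1 − p)d² to the between-patient variance, in units of the within-level variance.
- d = 0.5: 0.16 × 0.25 = 4% (20% above-knee) to 0.25 × 0.25 = 6% (50%).
- d = 1: 0.16 × 1 = 16% to 0.25 × 1 = 25%.

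**Step 5: effect of stratifying.** In a simulation of 50 patients with permuted blocks of 4 within level (assumed block size), the largest gap was about 8 points, and a gap of 12 points or more never occurred at any assumed share.

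**The case against.** The strongest reply is that this is ordinary chance variation in a small randomized trial. The unadjusted standard error already reflects it, and the plan limits interpretation to a pilot without power. The likely shift is also modest. Take a 20-point gap, a 20-point difference in healing failure between levels (assumed), and the 40% re-amputation or revision rate in the Study Abstract as an illustrative failure rate. The shift is 0.20 × 20 = 4 points, against a standard error of √(2 × 0.4 × 0.6/25), about 14 points: roughly 0.3 of a standard error. That stands, and it keeps this a matter of precision.

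It is also true that no section says above-knee and below-knee stumps differ in perfusion or healing. The factor the documents stress is diabetes. A reader might infer that level is the largest known source of variation in the outcomes; nothing in the documents supports that ranking.

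A reader might likewise infer that the record number determines the arm. The text says that the pharmacy knows that number, not that it fixes the assignment. Level is not among the items listed as withheld, and the undefined information sent to the pharmacy could include it. What remains is that no section says level is used.

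Perfusion has some protection. The day 0 fluorescence angiogram is taken in the operating room, before the first infusion, so a contrast of change from day 0 could remove part of a stable level difference. But the plan specifies no such contrast, and Statistical Methods lists day 0 among readings made after treatment. Healing gets no direct protection from it.

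Finally, if the later trial enrols both levels and does not adjust, variance that includes level is the right planning input. That argues for reporting both versions. It does not argue for leaving the term out.

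**Conclusion.** The point holds as one of avoidable imprecision. Two stump types are eligible, no stratification by level is described, and the model has no level term. Over assumed above-knee shares of 20% to 50%, a gap of 20 points or more has a chance of about 7% to 26% at 25 per arm (11% to 20% with independent binomials), and about 17% to 47% at 15 per arm (25% to 36%). If levels differ by 0.5 to 1 within-level SD, leaving level out enlarges the between-patient variance by 4% to 25% of the within-level variance. The share and the level effect are both assumptions, and the consequences shrink in proportion if level matters little.

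A reader might go further and call the comparison biased or the trial invalid. Neither follows: chance imbalance under randomization averages to zero. It can distort a single small trial, and an early unblinded look more so.

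**What to change.** 1. **Analysis, all patients.** Pre-specify planned amputation level as a fixed term in the perfusion and healing models. Fix it before any unblinding, including the interim, and apply it to patients already enrolled. Report the variance components and intra-class correlation with and without the term, so that the next trial can use whichever matches its own design.
2. **Allocation, patients still to be randomized.** Send the pharmacy the planned level and use separate above-knee and below-knee lists, with concealed blocks of varying size.

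The model term alone meets most of the concern if enrolment is well advanced.

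**Cost.** One degree of freedom, and two lists in place of one. A few patients whose level changes in surgery stay in their planned stratum. Assignments become slightly more predictable within blocks, which matters because the pharmacy's notices on MR eligibility (Rationale for the Selection of Outcome Measures) can already reveal an allocation when one arm's quota of three is full. Varying, concealed block sizes limit that but do not remove it.

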 1. CBC
 2. BMP
 3. HbA1C (Maybe obtained at some point during the course of the 6 day study if the patient did not have a value obtained within 3 month prior to the amputation)
 4. Pre-albumin (May be obtained at some point during the course of the 6 day study if the patient did not have a value obtained within 1 week prior to the amputation)
2. Research laboratory evaluation
 1. One sample within 12 hours from the time of the amputation operation, if possible
 2. One sample within 12 hours prior to discharge from the hospital or by POD5, if possible
 3. Samples will be taken to the research laboratory to evaluate:
 1. Serum Insulin level
 2. Serum Thiol Level
 3. Serum L-Cysteine level
 4. Serum lipidomics
 5. Serum nicotine and cotinine levels
 6. Other essential plasma/serum proteins or biomarkers

Contraindications to Measurement:

- Patient refusal/inability to participate in measurement before or at time of data collection (*a contraindication to anthropometric measurements does not exclude the patient from other measurements within the study protocol*).
- Severe anemia (Hematocrit < 22), that develops following enrollment in the study.

Data Analysis:

Anthropometric data will be analyzed to determine its effects on patient amputation stump healing score, qualitative peak perfusion, and/or quantitative peak perfusion.

D. MRI Measurements

Location of Procedure:

- Center for Clinical Imaging Research

Time of Data Collection:

- Postoperative Day 4, If possible and/or equipment available and if the patient is still in-house.

Contraindications to Measurement:

- Patient refusal/inability to participate in measurement before or during data collection
- Patient unable to lie supine for at least 30 minutes during measurement collection
- Contraindication to MR scanning such as intracranial vascular clips, pacemaker or intraocular metal.
- Patient is hemodynamically unstable, pregnant, are claustrophobic.

MRI Procedural Steps:

1. The patient is asked to lie supine on a narrow bed in the MRI scanner. An MRI scanner is a large donut-shaped machine that is used by thousands of hospitals to make pictures of various parts of the body. The patient is given ear plugs or earphones to dampen the loud noise the scanner makes when taking pictures. The patient is also given a squeeze ball which can activate an alarm at the scanner operator's console, so the patient can let the operator know to have a question or need assistance.

2. The patient is scanned under an existing non-contrast MRI protocol to obtain blood flow and tissue oxygenation pictures at rest.

3. Each study patient is carefully monitored by a physician, nurse practitioner, physician assistant or nurse for signs and symptoms of allergic reaction or intolerance to this non-invasive procedure until discharge.

Visit 1

Following patient discharge, amputation stumps will be evaluated within 20-50 days during a routine post-operative visit using the same anthropometric parameters (LAFA and TcPO₂ will not be performed at this time point).

Safety and Adverse Events

Safety and Compliance Monitoring

All study patients are inpatients at BJH in St. Louis Missouri and are cared for by appropriately trained nurses on the inpatient wards. Vascular surgery Attending Physicians, Vascular Surgery Fellows, Surgical Residents, and a team of Nurse Practitioners oversee their overall care. Inpatient ward nurses routinely assess patients at least every 4 hours with vital signs, intake and output measurements, pain assessment, nutrition assessments, medication review and administration, etc.

Medical Monitoring

Medical monitoring of the study will be performed by the Principal Investigator. The goal of monitoring this study is to enhance human subject protection and to monitor the quality of the clinical trial data by focusing investigator oversight on the most important aspects of study conduct and reporting. The PI will provide regular oversight to ensure adequate protection of the rights, welfare, and safety of the human subjects and the quality of the clinical trial data.

Definitions of Adverse Events

An adverse event (AE) is defined as any untoward medical occurrence in a subject administered a pharmaceutical product or who has undergone study procedures and which does not necessarily have a causal relationship with this treatment. An AE can therefore be any unintended sign (including an abnormal laboratory finding), symptom, or disease temporally associated with the use of the investigational product, whether or not related to the medicinal (investigational) product.

All AEs will be recorded in the CRF from the time of consent through the 30 days post-operative visit. AEs will be followed to resolution or stabilization.

An abnormality identified during a medical test (e.g., laboratory parameter, vital sign, physical exam) should be defined as an AE only if the abnormality meets one of the following criteria:

- Induces clinical signs or symptoms
- Requires active intervention
- Requires interruption or discontinuation of study medication
- The abnormality or investigational value is clinically significant in the opinion of the investigator.

An AE is considered “serious” if, in the view of the Investigator, it results in any of the following outcomes:

- Results in death
- Is life threatening (an AE is considered “life threatening” if, in the view of the investigator, its occurrence places the subject at immediate risk of death. It does not include an AE that, had it occurred in a more severe form, might have caused death)
- Results in persistent or significant disability/incapacity or substantial disruption of the ability to conduct normal life functions
- Results in congenital anomaly, or birth defect
- Requires inpatient hospitalization or leads to prolongation of hospitalization (hospitalization for treatment/observation/examination caused by AE is to be considered as serious)
- Other medically important events

Medical and scientific judgment should be exercised in deciding whether expedited reporting is appropriate in other situations, such as important medical events that may not be immediately life-threatening or result in death or hospitalization but may jeopardize the subject or may require intervention to prevent one of the other outcomes listed in the definition above. These events, including those that may result in disability/incapacity, should also usually be considered serious. Examples of such events are intensive treatment in an emergency room or at home for allergic bronchospasm or blood dyscrasias or convulsions that do not result in hospitalization.

Events related to the medicinal products administered to the subject as part of the study (e.g., study drug, comparator, background therapy) that may require expedited reporting, but are not limited to:

- Overdose of the medicinal product(s)
- Inadvertent or accidental exposure to the medicinal product(s)
- Medication error involving the medicinal product(s)

All AEs and events related to the medicinal product administered to the subject as part of the study will be recorded in the CRF from the time of consent through the 30 days post-operative visit. AEs should be followed to resolution or stabilization.

Classification of Events

AEs are classified as *serious or non-serious; expected or unexpected; and study-related, possibly study-related, or not study-related.*

Relationship

Defining Relationship

Adverse events that fall under either "Possible" or "Probable" should be defined as "AEs whose relationship to the study drugs could not be ruled out." Relationship to study drug will be assessed using the following criteria:

Not Related	A clinical event, including laboratory test abnormality, with a temporal relationship to drug administration, which makes a causal relationship improbable, and/or in which other drugs, chemicals or underlying disease provide plausible explanations.
Possible	A clinical event, including laboratory test abnormality, with a reasonable time sequence to administration of the drug, but which could also be explained by concurrent disease or other drugs or chemicals.
Probable	A clinical event, including laboratory test abnormality, with a reasonable time sequence to administration of the drug, unlikely to be attributed to concurrent disease or other drugs or chemicals, and which follows a clinically reasonable response on re- administration (re-challenge) or withdrawal (de-challenge).

Severity

Defining Severity

Grade 1 - Mild AE: Asymptomatic or mild symptoms, clinical or diagnostic observations noted; intervention not indicated.

Grade 2 - Moderate AE: Local or noninvasive intervention indicated.

Grade 3 - Severe AE: Medically significant but not immediately life threatening hospitalization or prolonged hospitalization

Grade 4 - Life-threatening: Life threatening consequences, urgent intervention indicated or disabling AE

Grade 5 – Death: Death related to AE

Expectedness

All AEs that are previously unobserved or undocumented are referred to as “unexpected,” in that their nature and severity are not consistent with information provided in the relevant product information (e.g., approved professional package insert or product label). Determination of expectedness is made by the Investigator on a case-by-case basis.

Data Collection Procedures for Adverse Events

All adverse events must be documented in the subject’s medical record and/or Case Report Form (CRF). In order to prevent bias collection of AEs, subjects should not be questioned regarding specific events that might be anticipated while on the study. AEs should be spontaneously reported or elicited from a subject using open-ended questioning during examination or evaluation.

The AE CRF will include the start date (and time if applicable; e.g. It may be important to time the AE, especially with infusion reactions), a detailed description of the event, any treatment for the AE (e.g., no treatment needed, further testing to diagnosis event, hospitalization, dose reduction, holding of study intervention), Investigators assessment of the AE (serious or not serious, expected or unexpected, related or unrelated) and the date the AE resolved. If an ongoing AE worsens or improves in its severity or its relationship to the study drug changes, documentation should be collected as above.

Reporting Procedures

Unanticipated problems and unexpected adverse drug events are defined below and will be reported to the local IRB according to local policy.

An Unanticipated problem involving risks to participants or others:

1. Are unexpected (in terms of nature, severity, or frequency) given (a) the research procedures that are described in the protocol-related documents, such as the IRB-approved research protocol and informed consent document; and (b) the characteristics of the subject population being studied.
2. Are related or possibly related to participation in the research.
3. Suggest that the research places participants or others at a greater risk of harm (including physical, psychological, economic, or social harm) than was previously known or recognized.

An unexpected adverse drug event:

1. Any adverse drug experience (associated with the use of the drug), the frequency, specificity, or severity of which is not consistent with the current investigator brochure or package insert; or
2. If an investigator brochure or package insert is not required or available, the specificity or severity of which is not consistent with the risk information provided to the participants and the IRB

Adverse Event Reporting Period

Per local IRB policy an individual adverse event that meets the definition of an anticipated problem involving risk to participants or others or an unexpected adverse drug event will be reported to the IRB within 10 working days. If an unexpected adverse drug event results in a death the event

will be reported to the IRB within 1 working day. Individual adverse events that do not meet the definition of an unanticipated problem involving risks to participants will be reported to the IRB at the time of continuing review (annual renewal).

Post-study Adverse Event

All AEs will be recorded in the CRF from the time of consent through the 30 days post-operative visit however all AEs will be followed to resolution or stabilization.

Study Outcome Measurements and Ascertainment

As described previously, study subjects will undergo evaluations using LAFA, TcP02, and anthropometric measurements.

Statistical Plan

Sample Size Determination and Power

The purpose of this study is to obtain sufficient preliminary data to determine the sample size necessary for a future large definitive clinical trial. For this pilot study, we plan to enroll 25 patients in each group, allowing for a dropout rate of 10% per group.

We emphasize that effect size (the expected difference in primary outcome between the treatment and control groups) should not be determined by the pilot study. Rather it is determined by the minimum clinically important difference. However, the effect size from the pilot give us some ideas about possible achievable difference.

Interim Monitoring and Early Stopping

An interim analysis will be conducted once >30 patients are enrolled in the study. Analysis will focus on determining differences between NAC and control group. Interim analysis will help determine early differences between the study groups and safety profile of study intervention. The investigators may end the study early depending on study findings, safety profile of the data, and/or if data is adequate for a peer-reviewed publication.

Analysis Plan

Data analysis include (1) the partition of variation of outcome measurements into within and between patient components to obtain standard deviation of measurements, intra-class correlation of the measurements, (2) use of appropriate regression model (GEE or mixed effect regression) to compare the outcome measurements between two groups, while accounting for the intra-class correlation. Interpretation of analysis should be made within the context of a pilot study where we have a pre-specified hypothesis but do not have power analysis for testing the hypothesis.

Statistical Methods

One of the main study outcomes (and in the future large study) is the stump perfusion assessment, which is a continuous variable measured three times (D0, D3, and D5) after

